Despite this, recently, a new retrospective review has been published in Annals of Oncology with 28 COVID-19 + oncology patients.⁽²⁰⁾ The most common tumor in this series was lung cancer (25%), with only 3 patients with genitourinary cancer (2 patients with prostate cancer and 1 patient with testicular cancer). The median age was 65 years. The most common symptoms were fever (82.1%) and cough (78.6%), and the most common laboratory abnormalities were lymphopenia (82.1%) and elevated CRP (82.1%). The risk of severe complications was higher in patients who had received oncological treatment in the 14 days prior to the diagnosis of the infection, with an HR in the multivariate analysis adjusted for age and sex of 4.079 (95% CI 1.086-15.322, p 0.037). However, despite being the largest series collected of COVID-19+ oncology patients, it has its limitations, which are mentioned in the article itself. To begin with, this is a retrospective study of 28 patients. Furthermore, the population is heterogeneous, with different tumors and stages (64.3% are stages I-III), which is not taken into account in multivariate analysis. A more recent article in Cancer Discovery with 69 patients with lung cancer, mainly active or metastatic (80%), determined that previous oncological treatment with Programmed Dead-1 (PD-1) blockers does not have a significant impact on severity of COVID-19 infection⁽²¹⁾.

23. Working hypothesis

The identification of patients with genitourinary tumors who suffer from infection with the SARS-CoV-2 agent can represent multiple benefits both for themselves and for health professionals and the health system itself. We would be able to know more precisely the clinical evolution of this type of patient, know their prognosis and be able to select the most appropriate treatment modality for future pandemics.

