3.2. Secondary objectives

- To evaluate the mortality associated with COVID-19 infection in the population with genitourinary tumors. Percentage of patients alive/dead at discharge.
- To evaluate the rate (percentage) of complications that have required hospital admission and/or ICU treatment.
- Describe the frequency of asymptomatic or minimally symptomatic COVID-19 infections. Percentage of asymptomatic patients or with mild symptoms included in the study.
- Evolution of the oncological disease. Impact/influence of COVID-19 infection on the effectiveness of oncological treatment. Data will be collected on delays/modifications in follow-up or oncological treatment regimens. The average delay time and the number of modifications will be evaluated. Likewise, it is expected to obtain data on time to progression and overall survival of cancer patients, which can be compared with the reference values for each type of tumor pathology.

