4.3. Inclusion criteria

- Patients ≥18 years old.
- Diagnosed with genitourinary cancer (urothelial, kidney, prostate and germ cell).
- COVID-19 infection prior to oncological treatment, during treatment or after treatment.
- COVID-19 infection must be confirmed by PCR or serology, regardless of whether or not the patient requires hospitalization due to the infection. Additionally, clinical and/or radiological determination must be available in those patients who present symptoms.

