4.4. Exclusion criteria

- Not applicable.

As this study is an EPA-AS, all the researchers' activities are carried out in accordance with the center's usual clinical practice. No withdrawal criteria have been established. Information from the clinical history will be collected as long as it does not exist on the part of the researcher, patient refusal to do so. Therefore, those patients who do not attend the corresponding visits will be declared as lost to follow-up, those patients who withdraw their consent to participate, the data collected up to that point will be used for statistical analysis, being lost to follow-up from which the patient withdraws his consent.

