5. VARIABLES

5.1. Study variables

A data collection notebook will be prepared in which the following variables will be collected for analysis:

Affiliation of the center:

- Hospital name
- Province
- Investigator's name
- Patient number

Patient characteristics:

- Age
- Sex
- Age
- Hospital center where the patient is recruited (in order to have epidemiological data on the pandemic that may be of interest)

Pathological history:

- Concomitant pathology (cardiac, pulmonary, renal, liver, Diabetes Mellitus, HIV, AI)
- Usual pharmacological treatment
- Smoking and alcohol habit

Tumor pathology:

- Tumor type, histology and stage (initial and at diagnosis of infection)
- Date of cancer diagnosis
- Active cancer treatment or follow-up
- Participation in clinical trial
- Type of treatment most recently received for the infection (Surgery; Radiotherapy; Chemotherapy: Drug, Immunotherapy, TD: Drug, HT: ADT alone or with Abiraterone, Enzalutamide, others)
- Treatment lines
- Start and last dose received of the most recent oncological treatment

For patients with prostate cancer:

- Local treatment and type (Surgery, Radiotherapy)
- Adjuvant ADT or advanced disease (start date)
- NAH (date and line of treatment)
- Associated corticosteroid treatment: Prednisone vs Dexamethasone (dose)

COVID-19 infection data:

- Confirmation date of COVID-19 infection
- PCR diagnostic test
- IgG or IgM serological diagnostic test
- Present symptoms

- Analytical alterations, lymphopenia, elevated CRP, high D-dimer.
- Thrombosis associated with COVID-19 infection
- Date of onset and disappearance of symptoms
- Days duration of fever and cough
- Radiological examination at the moment of greatest severity
- Complications of infection: presence of complications and/or hospital or ICU admission
- Admission date
- Date of most serious complication
- Treatments received for COVID-19
- Discharge status
- Fecha de alta / exit
- Negativization of the presence of viruses by PCR
- Negative PCR date

For patients who are receiving or have received immunotherapy treatments, additional information will be collected:

- Immunotherapy treatment line
- Start/end date of immunotherapy treatment
- Date of last dose received prior to COVID-19 infection
- Immunotherapy received as monotherapy or combination
- Type of immunotherapy
- Adverse effects

Prospective follow-up data (6 months from patient inclusion):

- Date of start or restart of oncological treatment after infection

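### Overall survival and time to progression are to be set against reference values by tumour type, in a cohort of all stages, lines and treatment phases, so a COVID-19 effect cannot be separated from case mix

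*Combined protocol and SAP*

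**What the plan says.** The last secondary objective (section 3.2, and item iv in the summary, section 1.2) is headed by the evolution of the oncological disease and names as its subject "Impact/influence of COVID-19 infection on the effectiveness of oncological treatment". It expects data on time to progression and overall survival, "which can be compared with the reference values for each type of tumor pathology". No source is given for these values, and no stage, setting or line is attached to them. No other comparator for the two outcomes appears in the document.

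The cohort is open. Section 4.3 requires a patient to be "Diagnosed with genitourinary cancer (urothelial, kidney, prostate and germ cell"), with "COVID-19 infection prior to oncological treatment, during treatment or after treatment". The entry for exclusion criteria in section 4.4 is "Not applicable".

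Section 4.5 plans a descriptive analysis, simple two-variable tests, Kaplan-Meier curves and the log-rank test. It mentions no stratified, adjusted or standardised analysis.

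Section 5.1 does collect what would be needed: "Tumor type, histology and stage (initial and at diagnosis of infection"), "Active cancer treatment or follow-up", and the number of treatment lines.

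**The concern.** Every patient has COVID-19, so the study has no uninfected group of its own. For overall survival and progression, the external reference is the only contrast that could speak to an effect of the infection.

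A reference value for a tumour type is an average over the stages and settings of whichever population produced it. The cohort is another such mixture. Section 5.1 shows that it can contain neoadjuvant patients, adjuvant and advanced hormone treatment, several treatment lines, and patients in follow-up only. Two populations with identical survival within each stage will differ overall if their stage shares differ.

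Against a reference drawn from advanced disease, real harm could be hidden. Against a reference of mainly localised disease, harm could appear where there is none. This holds even if both survival times are counted from the same starting point.

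**Working it through.** **Figure in the plan.** There is none to reproduce. The 250 patients are an expected number without a calculation, and no survival rate or reference value is stated.

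**Formula.** Let p_c and p_r be the share of stages I-III in the cohort and in the reference. Let S_E and S_A be 6-month survival in stages I-III and stage IV, equal in both populations, so that the true COVID-19 effect is zero. Then:

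- cohort survival = p_c × S_E + (1 − p_c) × S_A
- reference survival = p_r × S_E + (1 − p_r) × S_A
- apparent difference = (p_c − p_r) × (S_E − S_A)

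**Inputs.**

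- S_E = 97-99% and S_A = 75-85%. These are assumptions. The gap S_E − S_A runs from 0.97 − 0.85 = 0.12 to 0.99 − 0.75 = 0.24.
- p_c = 0.30 (assumption) or 0.643. The second is the stage I-III share that section 2.2.3 quotes for a 28-patient series with only 3 genitourinary cases. It serves as a worked value and is not a forecast for this cohort.
- p_r = 0 (all-advanced reference) or 0.80 (mainly early-stage reference). Both are assumptions.

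**Results**, in percentage points; a plus sign means the cohort looks better:

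| Cohort early-stage share | Reference early-stage share | p_c − p_r | × 0.12 | × 0.24 |
|---|---|---|---|---|
| 30% | 0% | +0.300 | +3.6 | +7.2 |
| 30% | 80% | −0.500 | −6.0 | −12.0 |
| 64.3% | 0% | +0.643 | +7.7 | +15.4 |
| 64.3% | 80% | −0.157 | −1.9 | −3.8 |

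For each cohort mix, the sign changes between the two references although COVID-19 has no effect.

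**Second model as a check.** Take exponential survival within stage, with assumed median overall survival of 60-120 months for early and 15-36 months for advanced disease, and a true hazard ratio of 1. For medians of 120 and 24 months, 6-month survival is 2^(−6/120) = 0.966 and 2^(−6/24) = 0.841.

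- Reference with 30% advanced: 0.7 × 0.966 + 0.3 × 0.841 = 0.928.
- Cohort with 70% advanced: 0.3 × 0.966 + 0.7 × 0.841 = 0.878.
- Apparent cumulative-hazard ratio: ln(0.878) / ln(0.928) = 1.75, from unrounded values.

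Over the four pairs of medians tried (120/36, 120/24, 120/15 and 60/24), this scenario gives 1.42 to 1.95. An all-advanced reference against a cohort with 60% advanced disease gives 0.62 to 0.75, an apparent benefit.

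**Effect of matching.** If p_c = p_r, the difference is zero and the ratio is 1.00, by construction.

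**Not calculated.** No figure was worked out for time to progression. For patients in follow-up without active treatment, progression on treatment has no clear meaning, and a treatment-based reference would not describe them.

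**The case against.** **The phrase may cover more than tumour type.** Section 5.1 uses tumour pathology as the heading of a block that includes histology, stage, treatment status and lines, so the reference might be meant to be specific on all of these. That is possible. The more natural reading of a reference for each type is urothelial, prostate, renal and testicular, and no text links stage or line to the comparison. Under either reading, the reference population needs to be specified.

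**The comparison is permissive and descriptive.** The wording allows a comparison without requiring one. No test, margin or decision rule is attached to it, section 4.5 calls the planned analysis descriptive, and no main objective depends on it. This stands and lowers the weight of the point. It does not remove the confounding, because this is the only contrast offered under an objective about impact.

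**Section 2.2.3 is not a direct parallel.** That section notes of an earlier series that "the population is heterogeneous, with different tumors and stages (64.3% are stages I-III), which is not taken into account in multivariate analysis". The remark concerns a model for severe complications, not an external survival reference. It shows that the sponsor accepts the principle, but the protocol does not contradict itself here.

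**Fine strata would be small.** Four tumour types by four settings (neoadjuvant or adjuvant, first-line advanced, later-line advanced, follow-up) give 16 cells, or 250 / 16 ≈ 16 patients each if evenly spread. This stands, and it is why standardisation should be allowed as an alternative.

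**Stronger readings.** A reader might infer that a stage difference will be reported as a COVID-19 effect. The documents do not say so; they support only that the two cannot be told apart. A reader might also infer that the choice of reference alone fixes the direction, or that the distortion always exceeds 5 points. Direction and size depend on both mixes, and the 64.3% cohort against the 80% reference gives only 1.9 to 3.8 points.

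**Conclusion.** The point holds in a limited form. As written, a difference between this cohort and a tumour-type reference value cannot be attributed to COVID-19, because stage, line and treatment phase are unrestricted in the cohort and unspecified in the reference.

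In the illustrations with no COVID-19 effect, the apparent difference in 6-month survival runs from 12.0 points worse to 15.4 points better. The smallest case is 1.9 points. These figures rest on assumed survival rates and stage shares. The documents give neither the cohort's mix nor the reference's, so the actual size and direction are unknown.

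The point is worth correcting because it is cheap to correct, but its severity is low: it concerns one sentence of a descriptive secondary objective.

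**What to change.** In sections 1.2 and 3.2, replace the sentence on reference values with wording to this effect, and add a matching line in section 4.5:

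> Overall survival and time to progression are compared with reference values only within tumour type by stage at infection and treatment setting or line, or with the reference standardised to the cohort's mix of these factors. Patients in follow-up without active treatment form their own stratum for overall survival and are left out of the time-to-progression comparison. Where no matched reference exists, or a stratum is below a minimum size fixed before analysis, results are described without comparison. No unstandardised comparison pooled over stage is attributed to COVID-19.

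The source of each reference value and the minimum stratum size should be recorded before the data are analysed.

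The cost is wording only, since stage at infection, treatment status and lines are already in section 5.1. The downside is that, with about 250 patients, fewer comparisons will be reported. Standardisation keeps more of them, but it needs references that publish results by stage and setting.

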4. STUDY METHODOLOGY

4.1. Study type and design

This is a national multicenter, observational, retrospective and prospective post-licensure (EPA-AS) study that will include patients with genitourinary tumors presenting with COVID-19 infection.

The study will be carried out in Spanish hospital centers, with principal investigators belonging to the medical oncology services of the SOGUG group (Spanish Genitourinary Oncology Group), who will act as sponsor. Once the patients are selected, the variables described in section 5 of this protocol will be collected and studied.

The study will use data obtained from the patient's medical history, with no plans to use other sources.

The assignment of a patient to a specific therapeutic strategy has already been decided in advance by the usual clinical practice of medicine; The decision to prescribe a specific treatment is clearly dissociated from the decision to include a patient in the study. No intervention, whether diagnostic or follow-up, will be applied to patients other than standard clinical practice. Epidemiological methods will be used to analyze the data collected.

4.2. Study population

The inclusion of a total of 250 patients with genitourinary tumors presenting with COVID-19 infection is expected, sufficient to respond to the objectives set by the study.

4.3. Inclusion criteria

- Patients ≥18 years old.
- Diagnosed with genitourinary cancer (urothelial, kidney, prostate and germ cell).
- COVID-19 infection prior to oncological treatment, during treatment or after treatment.
- COVID-19 infection must be confirmed by PCR or serology, regardless of whether or not the patient requires hospitalization due to the infection. Additionally, clinical and/or radiological determination must be available in those patients who present symptoms.

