3. OBJECTIVES

3.1. Main objectives

- Describe the population infected by COVID-19 with genitourinary tumors (urothelial cancer, prostate cancer, testicular cancer and renal cancer) treated in Spanish hospitals, know the clinical presentation, therapeutic evolution and prognosis of said intercurrent infectious process, as well as its possible relationship with different clinical and therapeutic factors.
- Assess the possible relationship of the different oncological treatments administered to these patients with the clinical evolution of COVID-19 infection, considering both patients who have undergone oncological treatment previously, during or after COVID-19 infection.
- To specifically evaluate the impact of COVID-19 infection on the toxicity of immunotherapy treatment (mainly pneumonitis) and the impact of immunotherapy on the evolution of the infectious condition in patients with tumors of genitourinary origin, in three different scenarios: during treatment, after treatment and in patients who are prescribed treatment after the infection has passed.
- Analysis of this same relationship in patients with genitourinary tumors and asymptomatic COVID-19 infection with positive Ab serologies (IgM and IgG).
- To evaluate in patients with Prostate Cancer (PCa) the impact of androgen deprivation therapy (ADT) and new antiandrogen agents (NAH) with or without corticosteroids on infection COVID-19.

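### Section 4.3 does not order the infection against cancer diagnosis, so patients whose tumour was found after COVID-19 ended can dilute the mortality percentage

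*Combined protocol and SAP*

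**What the plan says.** The eligibility rules are in protocol section 4.3. The cancer criterion is "Diagnosed with genitourinary cancer (urothelial, kidney, prostate and germ cell", with no date attached. The timing criterion is "COVID-19 infection prior to oncological treatment, during treatment or after treatment", so its reference point is treatment. The confirmation criterion is "COVID-19 infection must be confirmed by PCR or serology, regardless of whether or not the patient requires hospitalization due to the infection", so a past infection seen only on antibodies can qualify. The entry under section 4.4 is "Not applicable". Section 4.7 makes anyone who meets the inclusion criteria a case, and section 4.6 has cases included consecutively.

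Other sections suggest that the tumour is already known at infection. Section 4.1 describes "patients with genitourinary tumors presenting with COVID-19 infection", section 4.2 repeats that description, and the first main objective in 3.1 calls the infection intercurrent. Section 5.1 collects "Tumor type, histology and stage (initial and at diagnosis of infection", which presupposes a tumour to stage at that time.

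One main objective also looks beyond the infection. Immunotherapy is to be studied "in three different scenarios: during treatment, after treatment and in patients who are prescribed treatment after the infection has passed".

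Section 3.2 defines mortality as the percentage alive or dead at discharge. Section 4.5 plans descriptive summaries, unadjusted tests and Kaplan-Meier curves. It has no restriction or stratification by the order of cancer diagnosis and infection.

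**The concern.** A patient infected in spring 2020 whose renal tumour is first diagnosed that autumn satisfies every line of 4.3, because the infection came before any cancer treatment. To receive that diagnosis the patient had to survive the episode. Such patients add to the denominator of COVID-19 mortality and can add nothing to its numerator. They also were not known cancer patients when infected, so they do not inform prognosis in the population that 4.1 describes.

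Two results are at stake. The first is the whole-cohort mortality percentage. The second is the comparison in the second main objective, which relates oncological treatment to the course of infection. Every late-diagnosed patient falls in the group not treated at infection, so the dilution is concentrated in one arm.

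The sponsor already treats selective loss of deaths as a threat to validity: section 6.3 waives consent for patients who died before authorisation, to avoid that bias. The waiver does not touch this route.

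**Working it through.** **Inputs.** From the documents: about 250 patients (4.2 and 4.5), with no rate, precision target or power behind the number, so there is no sample-size calculation to reproduce. Assumed, because the documents give no values: m, mortality in patients with cancer known at infection; f, the share of the mortality denominator whose tumour was found after the episode ended; c and c_s, the complication rates in known-cancer and late-diagnosed patients.

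**Step 1, mortality.** Late-diagnosed patients contribute no deaths, so observed mortality = m(1 − f), and the relative understatement is f.

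| Assumed m | f = 2% | f = 5% | f = 10% | f = 20% |
|---|---|---|---|---|
| 10% | 9.8% | 9.5% | 9.0% | 8.0% |
| 20% | 19.6% | 19.0% | 18.0% | 16.0% |
| 30% | 29.4% | 28.5% | 27.0% | 24.0% |

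As counts at m = 20%, f = 10%: 225 × 0.20 = 45 deaths, and 45/250 = 18%.

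**Step 2, scale against sampling error.** The Wald 95% half-width at m = 20% is 1.96 × √(0.20 × 0.80/250) = 5.0 points. It is 3.7 points at m = 10% and 5.7 at m = 30%. With m = 20%, the bias is 0.4 points at f = 2%, 1.0 at 5%, 2.0 at 10% and 4.0 at 20%.

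**Step 3, tumours found during the episode.** These patients are still at risk of death. If a fraction g of a 10% late-diagnosed group is of this kind and has the same mortality, observed mortality = 0.20 × 0.90 + 0.10 × g × 0.20. This gives 18.0% at g = 0, 18.5% at g = 0.25 and 19.0% at g = 0.5.

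**Step 4, complications.** Observed rate = (1 − f)c + f·c_s, with c = 50% and f = 10%.
- Late-diagnosed patients resemble ordinary survivors, and every death had a complication: c_s = (0.50 − 0.20)/(1 − 0.20) = 37.5%, observed 48.75%.
- c_s = 50%: observed 50%.
- c_s = 80%, for example tumours seen on imaging during a COVID-19 admission: observed 53.0%.

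The sign depends on how the tumours came to light.

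**Step 5, treatment comparison.** Illustration with equal true mortality of 20%: 175 treated at infection (35 deaths) and 50 known but untreated (10 deaths). Adding 25 late-diagnosed survivors to the untreated group gives 10/75 = 13.3% against 35/175 = 20%. The ratio is 1.5 where the true ratio is 1.

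**Step 6, can the order be recovered?** Section 5.1 lists the dates of cancer diagnosis, infection confirmation, symptom onset and symptom disappearance. A filter on confirmation date alone fails in one case: a newly diagnosed patient whose past infection is then found by serology has a confirmation date after the cancer diagnosis and passes. Symptom onset resolves this where there were symptoms. For an asymptomatic serology-positive patient the order stays unknown.

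**The case against.** The best defence is that the protocol states its population several times: patients with genitourinary tumours who present with COVID-19. Read with that wording and with the staging variable, infection before oncological treatment naturally means cancer diagnosed but not yet treated. This is a fair account of the intent, and nothing shows that the sponsor set out to enrol late-diagnosed patients. But the descriptive wording is not an eligibility rule, section 4.7 makes the criteria decisive, and 32 centres must apply them. The ambiguity stands.

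The size may be small. The share is unknown, and the schedule in 4.9 (first centre in 3Q 2020, data extraction ending in 1Q 2021) limits how many patients could be infected, recover, be diagnosed and be included. At a 2% to 5% share the bias is far below the sampling error. That limits its importance, but the bias is systematic: a larger sample would not shrink it, and the confidence interval would not show it.

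It is also unclear whether never-admitted patients count in a percentage defined at discharge. If they do not, f is the share among those who do count.

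A reader might infer more than the documents support:
- That complication rates also fall and mild disease is overstated. Surviving does not mean avoiding admission, and step 4 gives either sign.
- That everyone diagnosed after infection is a certain survivor. This is true only for tumours found after the episode ended.
- That deaths with undetected tumours are missing. Those patients were never in the stated population; the problem is the survivors let in.

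**Conclusion.** The gap is real and worth closing. Sections 4.3, 4.4 and 4.7 together admit patients whose tumour was found after the COVID-19 episode, and section 4.5 does nothing to separate them. For that group the downward effect on mortality is certain by arithmetic, at a relative size of f. Its absolute size rests on assumed values of m and f: between 0.4 and 4.0 points at 20% mortality over shares of 2% to 20%, with nothing in the documents to support the upper end.

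For admission/ICU and asymptomatic percentages, only an uncertain effect can be claimed. The treated-versus-untreated comparison can be distorted more than the overall rate, because the late-diagnosed patients all sit on one side; the 1.5-fold figure is an illustration, not an estimate.

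**What to change.** State in 4.3 or 4.5 that the mortality, admission/ICU, asymptomatic and treatment-severity analyses are restricted to patients whose cancer diagnosis date is on or before the start of infection, defined as the earlier of symptom onset and first positive test.

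- Flag tumours diagnosed after that date and report them separately, distinguishing those found during the episode from those found after it ended. Keep them for the third main objective's description of treatment prescribed after infection; flagging serves that objective better than exclusion.
- Classify serology-only patients with no symptom date and a positive test around or after cancer diagnosis as of unknown order. Report them separately, and give the rates with and without them.

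The cost is small, because the cancer diagnosis, confirmation and symptom dates are already in 5.1. A few patients leave the severity denominators, including some whose tumour was found during the episode and who were at risk of death, which is why they need their own line. If 25 of 250 left, the half-width at 20% mortality would go from 5.0 to 1.96 × √(0.16/225) = 5.2 points.
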